#### 13.14 Publication

BBI acknowledges that the Investigator(s) have certain professional responsibilities to report to the scientific community on findings in clinical investigations they conduct. The Principal Investigator shall have the right to publish the results of research performed under this protocol, provided that such publication does not disclose any Confidential Information or trade secrets of BBI (other than the Clinical Data). If the Study is conducted as part of a multi-center protocol, Principal Investigator agrees not to independently publish his or her findings except as part of an overall multi-center publication, unless specifically approved in writing by BBI. The Principal Investigator agrees to, prior to submitting a manuscript, abstract, or any other written or oral presentation describing the Data for publication or presentation, forward to BBI a copy of the item to be submitted for publication or presentation. Upon reasonable request by BBI that is made within 30 days of receipt, the Principal Investigator agrees to withhold such publication an additional 60 days to permit the preparation and filing of related patent applications. In addition, BBI shall have the right to require the Principal Investigator to delete from any

publication or presentation any Confidential Information (other than the Clinical Data) of BBI and to require that any publication or presentation concerning the Study to acknowledge the Sponsor's support.

### 13.15 Research Outside the Terms of this Protocol

BBI has a legal responsibility to report fully to the regulatory authorities all the results of administration of its investigational drugs.

No investigative procedures other than those described in this protocol shall be undertaken on subjects enrolled in this study (unless required for the care of the subject), without the agreement of the IRB/Ethics Committee and BBI. The nature and results of any such procedures must be recorded and reported by a method agreed between BBI and the Investigator. The consent of the subjects must be obtained before any such procedures are undertaken.

The investigative drug provided to the Investigator for use under this protocol may not be used for any other purpose, including another study, compassionate use, or personal use.

# Boston Biomedical, Inc September 12, 2017 Clinical Protocol BBI608-503-103HCC

### 14 APPENDIX A: SCHEDULE OF ASSESSMENTS - PHASE IB

Tarta O Dana and James	Pre-Study	Study Evaluations					E-1-604-1-372-24				
Tests & Procedures	Evaluation	Cycle 1 C			Cy	Cycle 2 Cycle 3+		End of Study Visit			
Week	0	1	2	3	3	4	1	3	1	3	14- 30 days from last
Day	0	1	8	15	16	22	1	15	1	15	dose of study drug
Window	-5 (+ 2) days		± 2 day	s			± 2	day	± 2	day	
Medical history	X										
Physical examination	X			X			X		X		X
Serum pregnancy test 	X										
ECOG performance status	X			X			X		X		X
Vital signs, Weight, Height 	X	X	X	X		X	X	X	X	X	X
Hematology	X			X			X		X		X
Blood chemistry	X			X			X		X		X
Urinalysis	X			X			X		X		X
Child Pugh Class assessment	X										X
12-Lead electrocardiogram	X			$X^3$				$X^{10}$			
Serum AFP	X			X			X		X		X
Optional Tumor biopsy	$X^4$							X 			
Pharmacokinetics				X	X 			X			
Concomitant medications	X	X	X	X		X	X	X	X	X	X
Adverse events		X	X	X	X	X	X	X	X	X	$\mathbf{X}^7$
Dispense BBI608 or BBI503				X 			X		X		
Schedule 8-week Scan		X									
Tumor Measurements &	At baseline and then at every 8 weeks (56 days, ±7) beginning with										
staging	Cycle 1, Day 1						$X^8$				

<sup>1For women of child-bearing potential (WOCBP)

<sup>2Height will be assessed at pre-treatment (baseline) only

<sup>3ECG will be done **twice** on this day—once before the first dose of study drug is administered, and once ~ 3.5 hours (± 15 min) after study drug is administered.

<sup>4The pre-treatment (Baseline) optional tumor biopsy may be performed at any time prior to the first sorafenib dose on Cycle 1 Day 1

<sup>5If the on-study biopsy is performed on a day other than a PK day, then a single blood draw is needed within 30 minutes of the biopsy

 $^6\mathrm{For}$  patients in Arm 2 (BBI503 + sorafenib) only

<sup>7 Patients who are identified at the EOS visit as having persistent adverse events related to study drug (either BBI608 or BBI503) should continue to be followed on a monthly basis (or more frequently if clinically indicated) until resolution of study drug-related adverse events or until the AEs are deemed irreversible.

 If a patient discontinues protocol therapy due to radiologic progression of disease, an End of Study imaging assessment is not required

<sup>9 For ARM 2 only-BBI503 will be administered in the morning ONLY on C1D15 and in the evenings thereafter

 $^{10}\,\mathrm{ECG}$  will be done 3.5 hrs after study drug is administered

### Boston Biomedical, Inc September 12, 2017 Clinical Protocol BBI608-503-103HCC

### 15 APPENDIX B: SCHEDULE OF ASSESSMENTS - PHASE II

Tests & Procedures	Pre-Study	ly Study Evaluations					End of Study Visit			
Tests & Procedures	Evaluation	Cycle 1			Cycle 2 Cy			le 3+	End of Study Visit	
Week	0	1	2	3	4	1	3	1	3	14- 30 days from last
Day	0	1	8	15	22	1	15	1	15 	dose of study drug
Window	-5 ( + 2) days		± 2 days			± 2	day	± 2	day	
Medical history	X									
Physical examination	X			X		X		X		X
Serum pregnancy test 	X									
ECOG performance status	X			X		X		X		X
Vital signs, Weight, Height 	X	X	X	X	X	X	X	X	$X^6$	X
Hematology	X			$X^3$		X		X		X
Blood chemistry	X			$X^3$		X		X		X
Urinalysis	X			$X^3$		X		X		X
Child Pugh Class assessment	X									X
12-Lead electrocardiogram	X			X 			$X^{11}$			
Serum AFP	X			$X^3$		X		X		X
Optional Tumor biopsy	$\mathbf{X}^7$						X			
Pharmacokinetics							X 			
Concomitant medications	X	X	X	X	X	X	X	X	X 	X
Adverse events		X	X	X	X	X	X	X	X 	X 
Dispense BBI608 or BBI503 				$X^{10}$		X		X		
Schedule 8-week Scan		X								
Tumor Measurements & staging	At baseline and then at every 8 weeks (56 days, ±7) beginning with Cycle 1, Day 1				X 					

<sup>1 For Women of Child Bearing Potential

<sup>2 Height will be assessed at pre-treatment (baseline) only

<sup>3 For patients in Phase II who were randomized to receive sorafenib alone (Arm 3), labs may be obtained at any time on C1D15 (either before or after dosing with sorafenib on that day)

<sup>4 Applies only to patients randomized to either Arm I (BBI608 plus sorafenib) or Arm 2 (BBI503 plus sorafenib). Once the amendment 3 is in effect, Arm 2 in the Phase II portion will be closed for enrollment.

<sup>5 Single blood draw should be obtained in the morning for Arm 1 and Arm 2 only prior to the first dose of BBI608 or BBI503. Once the amendment 3 is in effect, Arm 2 in the Phase II portion will be closed for enrollment.

2

<sup>6 For patients in Phase II, C3D15 visits (and Day 15 visits of each subsequent cycle) need not be in person. In this case, the patient should be contacted by phone. Vital signs and weight need not be taken.

<sup>7 Optional tumor biopsy may be performed at any time between the screening visit and administration of the first sorafenib dose on Cycle 1 Day 1.

<sup>8 If a patient discontinues protocol therapy due to radiologic progression of disease, an End of Study imaging assessment is not required

<sup>9 Patients who are identified at the EOS visit as having persistent adverse events related to study drug (either BBI608 or BBI503) should continue to be followed on a monthly basis (or more frequently if clinically indicated) until resolution of study drug-related adverse events or until the AEs are deemed irreversible.

<sup>10 For ARM 2 only-BBI503 will be administered in the morning ONLY on C1D15 and in the evenings thereafter. Once the amendment 3 is in effect, Arm 2 in the Phase II portion will be closed for enrollment.

<sup>11 for phase II 12 Lead ECG should be performed pre dose BBI608 on C1D15 and after dose of BBI608 on C2D15.

# 16 APPENDIX C: PERFORMANCE STATUS

ECOG Performance status Scale			Karnofsky Performance Scale			
Grade	Descriptions	Percent	Description			
	Normal activity. Fully active, able to carry	100	Normal, no complaints, no evidence of disease.			
0	on all pre-disease performance without restriction.	90	Able to carry on normal activity; minor signs or symptoms of disease.			
Symptoms, but ambulatory. Restricted in physically strenuous activity, but		80	Normal activity with effort; some signs or symptoms of disease.			
1	ambulatory and able to carry out work of a light or sedentary nature (e.g., light housework, office work).		Cares for self, unable to carry on normal activity or to do active work.			
2	In bed <50% of the time. Ambulatory and capable of all self-care, but unable to carry	60	Requires occasional assistance, but is able to care for most of his/her needs.			
	out any work activities. Up and about more than 50% of waking hours.	50	Requires considerable assistance and frequent medical care.			
	In bed >50% of the time. Capable of only		Disabled, requires special care and assistance.			
3	limited self-care, confined to bed or chair more than 50% of waking hours.	30	Severely disabled, hospitalization indicated. Death not imminent.			
4	100% bedridden. Completely disabled. 4 Cannot carry on any self-care. Totally	20	Very sick, hospitalization indicated. Death not imminent.			
	confined to bed or chair.		Moribund, fatal processes progressing rapidly.			
5	Dead.	0	Dead.			

Table 4 PFS (Primary Definition) Censoring Reasons and Hierarchy 28

Table 5 PFS Censoring Reasons and Hierachy 29

VERSION HISTORY

This is the amendment version 2.4 of the statistical analysis plan (SAP).

Version	Date	Author(s)	Summary of Changes/Comments
Version 1.0	14SEP2018	[name]	Statistical Analysis Plan
Amendments 2.0-2.3	30AUG2019	[name]	
 1. Entire document: Updated study drug name BBI608 to napabucasin; BBI503 to amcasertib 2. Section 2: Updated efficacy endpoints: ORR, DCR and PFS will be derived using both RECIST 1.1 and mRECIST 1.1. 3. Section 5: Deleted Enrolled population. Added response evaluable analysis set and dose escalation evaluable analysis set. 4. Section 7: Specified that data will be summarized by phase, arm, and assigned dose level. 5. Section 7: Updated the duration of follow-up. 6. Section 7: Deleted the “treatment compliance” in the exposure summaries, because it will be covered by the analysis of relative dose intensity. 7. Section 7: Added “Adverse Events of Clinical Relevance” in the Adverse Event summaries. 8. Section 7: Laboratory data will not be summarized by visit level. Data will be presented in listings. 9. Section 7: Added physical exam. 10. Section 7: Added separate AE summaries for the Run-in period.
Amendment 2.4	27MAR2020	[name]	
Minor revisions to Section 5.3 (definition of Response Evaluable Set) to make wording more clear.
 
Added a new summary table for concomitant medication using preferred base.

Amendment 2.5	10SEP2020	[name]	Clarification of presentation of PK/PD data (Section 7.2.3.1). Specified the method used to identify AEs leading to study drug discontinuation (Section 7.2.4.2).
------------------	-----------	-----------------	---

List of Abbreviations

Abbreviation	Term
AEs	Adverse Events
AECR	Adverse event of clinical relevance
AFP	Alpha-feto protein
ALT	Alanine aminotransferase
ALP	Alkaline phosphatase
AST	Aspartate aminotransferase
ATC	Anatomical Therapeutic Chemical
BOR	Best overall response
BP	Blood pressure
BUN	Blood urea nitrogen
CI	Confidence interval
CO ₂	Carbon dioxide
CR	Complete response
CSR	Clinical study report
CTCAE	Common terminology criteria for adverse events
CV	Coefficient of variation
DBP	Diastolic blood pressure
DCP	des-gamma-carboxy prothrombin
DCR	Disease control rate

DI	Dose intensity
DLT	Dose-limiting toxicity
ECOG	Eastern Cooperative Oncology Group
ECG	Electrocardiogram
eCRFs	Electronic case report forms
EOT	End of treatment
HCC	Hepatocellular carcinoma
INR	International normalized ratio
ITT	Intent to Treat
LDH	Lactate Dehydrogenase
KM	Kaplan-Meier
LLQ	Low limit of quantification
MedDRA	Medical Dictionary for Regulatory Activities
mRECIST	Modified Response evaluation criteria in solid tumors
MTD	Maximum tolerated dose
NCI	National Cancer Institute
NE	Not Evaluable
OS	Overall survival
ORR	Objective response rate
PD	Progressive disease
PFS	Progression-free survival
PK	Pharmacokinetic
PR	Partial response
PT	Preferred term
RBC	Red Blood Cell
RD	Relative dose
RDI	Relative dose intensity
RECIST	Response evaluation criteria in solid tumors
RP2D	Recommended phase II dose
SAE	Serious adverse event
SBP	Systolic blood pressure
SD	Stable disease
SMQ	Standardized MedDRA Query

SOC	System Organ Class
TEAE	Treatment-emergent adverse event
WBC	White Blood Cell
WHO-DD	World Health Organization Drug Dictionary

1. INTRODUCTION

This statistical analysis plan (SAP) describes the statistical methods that will be used for the analyses of the clinical study report (CSR) for Boston Biomedical Protocol BBI608-503-103HCC. This SAP should be read in conjunction with the study protocol and electronic case report forms (eCRFs). This version of the SAP has been developed using Protocol amendment 4, dated 03Apr2018 [1].

1.1. Study Design

Phase Ib

This is an open label, phase 1b dose escalation study of napabucasin (BBI608) administered in combination with sorafenib (Arm 1), and amcasertib (BBI503) administered in combination with sorafenib (Arm 2) to patients with advanced hepatocellular carcinoma (HCC). Eligible patients will be randomized to either Arm 1 or Arm 2. The study is designed to explore the safety, tolerability and pharmacokinetics (PK) of napabucasin and amcasertib, and to define a recommended Phase II dose (RP2D) of napabucasin and amcasertib when administered in combination with sorafenib.

In Arm 1, initially 3 patients will be enrolled at napabucasin Dose-Level 1. Dose escalation will proceed with cohorts of 3 to 6 patients according to the criteria for dose escalation and the criteria for determining dose-limiting toxicity (DLT).

Napabucasin Dose Level	Napabucasin Dose & Schedule
Napabucasin Dose-Level I	160 mg Twice Daily
Napabucasin Dose-Level II	240 mg Twice Daily

In Arm 2, initially 3 patients will be enrolled at amcasertib Dose-Level 1. Dose escalation will proceed with cohorts of 3 to 6 patients according to the criteria for dose escalation and the criteria for determining DLT.

Amcasertib Dose Level	Amcasertib Dose & Schedule
Amcasertib Dose-Level I	100 mg Once Daily
Amcasertib Dose-Level II	200 mg Once Daily

Prior to initiation of combination therapy in each arm, sorafenib will be administered as monotherapy starting on Cycle 1, Day 1 for 14 days. Sorafenib will be administered at a fixed dose of 400 mg twice daily (800 mg total daily dose) for each arm and for each dose-level cohort. Dose-adjustment of sorafenib according to the approved product label is allowed. Following the sorafenib run-in period, the combination regimen will begin on Cycle 1, Day 15. Protocol therapy will continue in repeating 28-day cycles until disease progression, unacceptable toxicity, or another discontinuation criterion is met.

For both arms, PK assessments will be performed on Cycle 1, Day 15 and Cycle 2, Day 15. An additional PK assessment may be performed to confirm exposure following dose modification. Once the RP2D is determined for both study arms, the phase II portion will begin.

Phase II

The phase II portion is an open-label, 3-arm, randomized phase II trial of patients with advanced HCC who have not received prior systemic treatment. Patients will be randomized to receive either Arm 1: sorafenib administered in combination with napabucasin (at the RP2D determined for napabucasin plus sorafenib during the phase Ib portion); Arm 2: sorafenib in combination with amcasertib (at the RP2D determined for amcasertib plus sorafenib during the phase Ib portion), or Arm 3: sorafenib alone at a starting dose of 400 mg twice daily. The starting dose for sorafenib is the same for all study arms.

When protocol amendment 3 [2] is in effect, Arm 2 in the Phase II portion was closed for enrollment due to amcasertib portfolio priorities and to increase efforts in enrolling patients to Arms 1 and 3.

At the time amendment 3 was in effect, there were approximately 10 patients already enrolled in Arm 2. Therefore, the actual sample size in Phase II by the end of the study is projected to be approximately 70 patients after amendment 3. Protocol therapy will continue in repeating 28-day cycles until disease progression, unacceptable toxicity, or another discontinuation criterion is met. Pharmacodynamic assessments will be performed in patients with readily accessible tumors through an optional on-study tumor biopsy. Archival tissue, if available, will be collected from all patients. Throughout the study, safety and tolerability of napabucasin in combination with sorafenib and of amcasertib in combination with sorafenib will be assessed for the duration of study treatment and up to 30 days after discontinuation of study drug (either napabucasin or amcasertib).

Evaluation of anti-tumor activity will be performed at regular 8-week intervals, with the first assessment 8 weeks (56 days) after Cycle 1, Day 1. The radiologic assessments will be evaluated according to response evaluation criteria in solid tumors (RECIST) 1.1 and modified RECIST (mRECIST) for patients with HCC. Alpha-feto protein (AFP) measurements will be performed at baseline, at the end of the 2-week sorafenib monotherapy Run-In, and at the start of each subsequent study cycle.

1.2. Study Objectives

1.2.1. Primary Objectives

Phase Ib

To determine the safety, tolerability, and RP2D of napabucasin administered in combination with sorafenib and of amcasertib administered in combination with sorafenib in adult patients with advanced HCC who have not received prior systemic chemotherapy.

Phase II

To evaluate the tolerability, safety, and preliminary anti-tumor activity in patients with advanced HCC randomized to receive treatment with sorafenib in combination with napabucasin, sorafenib in combination with amcasertib, or sorafenib alone; napabucasin and amcasertib would be administered at their respective RP2D dose levels for combination administration with sorafenib, which were determined during phase Ib.

1.2.2. Secondary Objectives

The secondary objectives of this study are as follows:

- To determine the PK profile of napabucasin administered in combination with sorafenib and of amcasertib administered in combination with sorafenib.
- To perform biomarker studies for napabucasin administered in combination with sorafenib and for amcasertib administered in combination with sorafenib.

2. ENDPOINTS AND COVARIATES: DEFINITIONS AND CONVENTIONS

2.1. Primary Endpoint(s)

Phase Ib

- Dose-Limiting Toxicities (DLTs): For definition of DLT, see section 3.10 of the Protocol [1].

Phase II

- Objective Response Rate (ORR) and Disease Control Rate (DCR).

ORR is defined as the percentage of patients with a best overall response (BOR) of complete response (CR) or partial response (PR), using both RECIST and mRECIST assessment data.

DCR is defined as the percentage of patients with a best overall response (BOR) of complete response (CR) or partial response (PR) or stable disease (SD), using both RECIST and mRECIST assessment data. Response Criteria by RECIST and mRECIST is provided in Appendix 1.1 and 1.2, respectively. The categorizations of response (CR, PR, SD, progressive disease [PD], and not evaluable [NE]) and the derivations of BOR are provided in Appendix 1.3.

2.2. Secondary Endpoints

- Plasma concentration of napabucasin administered in combination with sorafenib.
- Plasma concentration of amcasertib administered in combination with sorafenib.
- Pharmacodynamics parameters (or biomarkers level in archival tissues) of napabucasin administered in combination with sorafenib.
- Pharmacodynamics parameters (or biomarkers level in archival tissues) of amcasertib administered in combination with sorafenib.

- Progression-Free Survival (PFS) by both RECIST and mRECIST in phase II.

PFS is defined as the time from the date of randomization to the date of first documentation of PD or death due to any cause, whichever occurs first.

PFS censoring rules are provided in Appendix 1.4: Censoring for Time-to-Event Data.

- Overall Survival (OS)

OS is defined as the time from the date of randomization to the date of death. Patients without documentation of death at the time of analysis will be censored at the date last known to be alive.

2.3. Other Endpoints

2.3.1. Adverse Events

- Adverse events (AEs) characterized by type, frequency, severity (graded by National Cancer Institute Common Terminology Criteria for Adverse Events [NCI CTCAE version 4.0]), timing, seriousness, and relationship to study therapy.
- Laboratory abnormalities characterized by type, frequency, severity (graded by NCI CTCAE version 4.0), and timing.

2.4. Covariates

Demographic and baseline disease characteristics may be considered as covariates in population PK, PK/pharmacodynamic (biomarker), and anti-tumor efficacy exploratory analyses.

3. HYPOTHESES AND DECISION RULES

3.1. Statistical Hypotheses

There is no hypothesis testing in this study.

3.2. Statistical Decision Rules

3.2.1 Dose Escalation and De-escalation

Dose escalation decisions are based on the observed number of patients with a DLT.

Table 1 Dose Escalation Decision Rules

Number of Patients with DLT at a Given Dose Level	Escalation Decision Rule
0 out of 3	Enter 3 patients at the next dose level
≥ 2	Dose escalation will be stopped. This dose level will be declared the maximally administered dose (highest dose administered). Three (3) additional patients will be entered at the next lower dose level if only 3 patients were treated previously at that dose.
1 out of 3	Enter at least 3 more patients at this dose level. 
 • If 0 of these additional 3 patients experience a DLT, proceed to the next dose level • If 1 or more of these additional 3 patients experience a DLT, then dose escalation is stopped, and this dose is declared the maximally administered dose. Three (3) additional patients will be entered at the next lower dose level if only 3 patients were treated previously at that dose.
≤ 1 out of 6 at highest dose level below the maximally administered dose	This is the maximally tolerated dose. RP2D will not exceed the maximum tolerated dose (MTD).

3.2.2. MTD and RP2D

The maximum tolerated dose (MTD) for a given combination arm is defined as the dose level at which no more than 1 patient with a DLT is observed among 6 patients for each combination. RP2D will be determined according to safety, tolerability, and pharmacokinetics.

3.2.3. Sample Size Justification

Phase Ib

The sample size for this study was determined by clinical rather than statistical considerations. With cohort sizes of 3 to 6 patients during phase Ib, if the true underlying rates of DLT at a given dose-level are 0.1, 0.2, 0.3, 0.4, and 0.5, there will be 91%, 71%, 49%, 31%, and 17% chances, respectively, of escalating to the next full dose.

Phase II

There is no statistical hypothesis testing and the sample size of the phase II part of the study is considered to be clinically adequate to assess tolerability, safety, and preliminary anti-cancer activity of the study drug of interest. Estimation and 95% confidence intervals will be provided for the proportion of patients with Grade 3 AEs by treatment, as well as for the proportion of patients who are alive and progression-free at 4 months (PFS-4) after randomization for each arm. Other anti-cancer activity parameters will also be estimated.

4. INTERIM ANALYSES

No formal interim analyses are planned for this study.

5. ANALYSIS SETS

5.1. Intent to Treat (ITT) Analysis Set

The ITT population includes all randomized patients.

5.2. Safety Analysis Set

The safety population is defined as all patients who receive at least 1 dose of napabucasin, amcasertib, or sorafenib. The safety population will be used for all safety-related analyses such as AEs, laboratory tests, and vital signs.

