## Note:

After the amendment 3 was in effect, Arm 2 in the Phase II portion was closed for enrollment due to BBI503 portfolio priorities and to increase efforts in enrolling patients on to Arm 1 and 3.

At the time of the amendment 3 being in effect, there were approximately 10 subjects enrolled in Arm 2 and approximately 30 patients remains to be the targeted sample size in each of the two open remaining arms, therefore, the total actual sample size in Phase II in the end is projected to be approximately 70 patients after the amendment 3.

# 5.4 On-Study Evaluation & Assessment Schedule | Cycle 1

The patient will be administered sorafenib monotherapy for the first two weeks of Cycle 1, which can also be termed "sorafenib run-in". The goal of the run-in period is to establish the tolerability of sorafenib prior to initiating combination therapy with study drug (either BBI608 or BBI503).

\*These do not need to be repeated if they were done within 7 days of this visit

\*\*Imaging obtained that meets these specifications can be used as the baseline assessment if it was obtained within two weeks  $\pm$  7 days of Cycle 1, Day 1.

Sorafenib will be obtained by the patient during this study as a standard-of-care medication; sorafenib will not be provided by study Sponsor.

Time required for the patient to initially obtain sorafenib should be taken into consideration when scheduling screening evaluations. Throughout the study, sorafenib will be supplied as a standard of care medication, guided by institutional and manufacturer policy.

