### 10.6 Safety Analysis

Safety and adverse events will be summarized for all enrolled patients in the phase Ib portion, phase II portion, and for the study overall. In addition, all patients receiving at least one dose of study drug (either BBI608 or BBI503) will be considered in the study drug safety population. Safety and adverse events will be summarized for the study drug safety population of phase Ib, phase II, and overall.

During the phase Ib portion of the study, adverse events will be summarized by dose-level and overall by arm. The numbers of patients enrolled, number with DLT, and number evaluable for determination of dose-escalation at each dose-level by arm will be reported. In addition to the evaluation and categorization of adverse events, listings of laboratory test results collected at baseline and during the study will be generated. Descriptive statistics summarizing the changes in those laboratory tests over time will be presented.

Adverse events will be graded according to the NCI CTCAE, version 4.0. The incidence of adverse events will be evaluated for each cohort. Patients will be followed for adverse events for at least 30 days after the last dose of study drug (either BBI608 or BBI503), or until they have recovered from all related study drug (either BBI608 or BBI503) adverse events.

Safety and adverse events will be reported by study arm for the intent to treat population and for all enrolled patients during the phase II portion of the study.

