7.2.4. Safety Analyses

All safety analyses will be summarized based on the safety analysis set.

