7.2.4.1. Adverse Events

Overall Summary of AEs

An AE will be regarded as **treatment-emergent**, if:

- it occurs on the day of or after the first dose of napabucasin or amcasertib or a combination drug and up to 30 days after the last dose of any study drug; or
- it occurs prior to first dose date of napabucasin or amcasertib or a combination drug and worsens in severity on therapy and up to 30 days after the last dose of study drug.

Adverse events will be coded by SOC and PT using the MedDRA v19.0. The severity of AEs will be graded by the investigator using (NIH NCI CTCAE Version 4.0). The verbatim term will be included in the AE listings.

An overview of treatment-emergent adverse events (TEAEs) will be provided. The number and percentage of patients will be summarized for:

- Patients with at least one TEAE
- Patients with TEAEs of CTCAE Grade 3 or higher
- Patients with serious TEAEs
- Patients with napabucasin-related TEAEs

- Patients with napabucasin-related TEAEs of CTCAE Grade 3 or higher
- Patients with amcasertib-related TEAEs
- Patients with amcasertib-related TEAEs of CTCAE Grade 3 or higher
- Patients with sorafenib-related TEAEs
- Patients with sorafenib-related TEAEs of CTCAE Grade 3 or higher
- Patients with napabucasin-related serious TEAEs
- Patients with napabucasin-related serious TEAEs of CTCAE Grade 3 or higher
- Patients with amcasertib-related serious TEAEs
- Patients with amcasertib-related serious TEAEs of CTCAE Grade 3 or higher
- Patients with sorafenib-related serious TEAEs
- Patients with sorafenib-related serious TEAEs of CTCAE Grade 3 or higher
- Patients with TEAEs leading to napabucasin dose hold
- Patients with TEAEs leading to dose reduction of napabucasin
- Patients with TEAEs leading to amcasertib dose hold
- Patients with TEAEs leading to dose reduction of amcasertib
- Patients with TEAEs leading to sorafenib dose hold
- Patients with TEAEs leading to dose reduction of sorafenib

Summary of AEs during Run-in Period

Besides overall summary of AEs as described above, the analysis of AEs during Run-in period will be summarized separately. Run-in Period is defined from the first sorafenib dose date to one day prior to patient administrated the napabucasin/amcasertib, or to the end of treatment if patient discontinued the study treatment before the napabucasin/amcasertib administration. For Phase II sorafenib monotherapy arm patients, run-in period is defined as the first 14 days of sorafenib administration.

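### The SAP leaves out the protocol's adverse-event summary in patients who actually took napabucasin or amcasertib, and plans no table for the combination period

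*SAP*

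**What the plan says.** **Protocol.** Section 10.1 defines a Study Drug Safety Population. Section 10.6 repeats the definition: "all patients receiving at least one dose of study drug (either BBI608 or BBI503) will be considered in the study drug safety population". It then requires an analysis on it: "Safety and adverse events will be summarized for the study drug safety population of phase Ib, phase II, and overall". This is additional to a wider summary, which the same section also requires: "Safety and adverse events will be summarized for all enrolled patients in the phase Ib portion, phase II portion, and for the study overall". Under Section 10.1 a patient counts as enrolled from the first sorafenib dose on Cycle 1, Day 1. For Phase II, Section 10.6 also wants safety by arm for the intent-to-treat and enrolled patients. Section 5.4 gives the reason for the sorafenib-only fortnight: "The goal of the run-in period is to establish the tolerability of sorafenib prior to initiating combination therapy with study drug".

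**SAP.** Section 5 lists four analysis sets: ITT, safety, response evaluable and, for Phase Ib, dose escalation evaluable. None is the Study Drug Safety Population. Section 5.2 reads: "The safety population is defined as all patients who receive at least 1 dose of napabucasin, amcasertib, or sorafenib". Section 7.2.4 adds: "All safety analyses will be summarized based on the safety analysis set". Section 7.2.4.1 sets the treatment-emergent window in these words: "it occurs on the day of or after the first dose of napabucasin or amcasertib or a combination drug and up to 30 days". That window therefore opens with the first sorafenib dose. The same section then says: "Besides overall summary of AEs as described above, the analysis of AEs during Run-in period will be summarized separately". The overall and run-in tables are the only two periods for which adverse-event tables are planned.

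**The concern.** The protocol separates two questions: what happens to everyone who starts therapy, and what happens to those who receive an investigational drug. The SAP answers only the first. A patient randomised to Arm 1 who stops during the run-in never takes napabucasin, yet stays in the Arm 1 denominator, including for the rows on napabucasin-related events. An event on Day 5 of sorafenib alone also enters the overall Arm 1 table, next to events on the combination.

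Safety and tolerability belong to the primary objective in both phases. The proportion of patients with a Grade 3 event, with a 95% interval, is the safety estimate that Protocol 10.5 and SAP 3.2.3 name for Phase II. With about 30 patients per arm, a few patients who leave or have an event in the first 14 days can move it visibly. A reader who wants the toxicity of the combination would not find it in the planned output.

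**Working it through.** **The plan's own figures.** The documents state no figure on this point. Their only calculated figures are the Phase Ib escalation probabilities, (1−p)³ + 3p(1−p)²·(1−p)³. For p = 0.1 to 0.5 these give 90.6%, 70.9%, 49.4%, 30.9% and 17.2%, which match the stated 91%, 71%, 49%, 31% and 17%. Nothing below depends on them.

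**Inputs.** The arm size is 30 (Protocol 10.3). Intervals are exact 95% (SAP 7.1.2). The documents give no run-in dropout or run-in event rate, so I assume 12 patients with a Grade 3 event on the combination, 0 to 6 leavers, and 0 to 6 patients whose only Grade 3 event is in the run-in.

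**Step 1: unexposed patients in the denominator.** With k run-in leavers who have no event, the planned table shows 12/30 and the rate among exposed patients is 12/(30−k). The planned figure is 12/30 = 40.0% (22.7 to 59.4) throughout.

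| Leavers k | Rate among exposed (95% CI) |
|---|---|
| 1 | 12/29 = 41.4% (23.5 to 61.1) |
| 3 | 12/27 = 44.4% (25.5 to 64.7) |
| 6 | 12/24 = 50.0% (29.1 to 70.9) |

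For events attributed to napabucasin or amcasertib, a leaver should contribute none, so the reported rate is the exposed rate times (30−k)/30. With 3 leavers the factor is 27/30 = 0.90. For all-cause events a leaver may have an event on sorafenib, so the table shows the most that dilution could do at each k.

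**Step 2: run-in events in the numerator.** With nobody leaving and r patients whose only Grade 3 event is in the run-in, the planned overall figure is (12+r)/30, while the combination-period rate stays at 40.0%.

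- r = 3: 15/30 = 50.0% (31.3 to 68.7)
- r = 6: 18/30 = 60.0% (40.6 to 77.3)

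Steps 1 and 2 act in opposite directions and can cancel. With k = 6 and r = 3, the planned table gives 15/30 = 50.0% and the combination-period rate is 12/24 = 50.0%. So the sign of the gap cannot be predicted.

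**Step 3: can the reader subtract the run-in table?** No, because one patient can have events in both periods. Suppose 15 of 30 patients have an event overall, 6 of them appear in the run-in table, and all 30 go on to the combination. The number with an event on the combination is then at least 15 − 6 = 9 and at most 15, that is 30.0% to 50.0%.

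**Step 4: the comparison of Arm 1 with Arm 3.** Phase II patients are randomised first and start therapy within 72 hours (Protocol 4.3). All arms start sorafenib at the same dose (Protocol Table 2). SAP 7.2.4.1 defines a 14-day run-in for Arm 3 as well. Run-in events and leavers are therefore expected alike in both arms. Equal numbers of run-in-only patients leave the difference in percentage points unchanged and pull the ratio toward 1. A patient already counted in the run-in is not counted again for a later event, which can narrow the difference. That blurs a contrast but does not favour an arm.

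**The case against.** The strongest reply is that the SAP's safety set is what the protocol asks for. Protocol 10.6 wants summaries for enrolled patients, defined by the first sorafenib dose, and the SAP set is essentially that group. This stands. The any-dose set is not an error and should not be replaced.

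A reader might go further and infer that early sorafenib toxicity biases Arm 1 against Arm 3. The documents do not support that, because randomisation precedes a sorafenib start common to all arms (Step 4). A comparison restricted to Day 15 onward would be the weaker one for that purpose, since it conditions on completing the run-in in an open-label trial.

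Two more points have partial force. First, Protocol 10.6 names a population and no onset window, so restoring the population would not by itself remove run-in events. The combination-period table goes beyond the protocol's text, although it follows from the stated purpose of the run-in. The population also has no Arm 3 members, so any Arm 3 reference group is a new choice. Second, the SAP tabulates run-in events separately and gives drug-related rows. These help, but the rows rest on investigator attribution in an open-label trial, treat missing relationships as related, and keep the wider denominator.

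Nor should one infer that the dose decision is distorted. Run-in events cannot be DLTs (Protocol 4.6), non-DLT leavers may be replaced, and escalation has its own evaluable set.

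**Conclusion.** The point holds as an omission. The protocol requires a safety summary among patients exposed to an investigational drug, and the SAP has neither the set nor any table that begins with exposure. Incidence on the combination is therefore unreported and cannot be derived from the planned tables, and the drug-related percentages can include unexposed patients.

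The size is unknown. Under the assumed ranges, leavers lower the reported Grade 3 rate by 0 to 10 points and run-in-only events raise it by 0 to 20. One leaver moves it by only 1.4 points (40.0% to 41.4%), well inside the interval. If almost everyone completes the run-in without a severe event, the effect is negligible. The trial is descriptive with no hypothesis test, so no formal conclusion is at risk. What is at stake is whether a primary safety objective can be read from the output.

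The run-in figures also depend on what is recorded. Protocol 8.1.1 starts adverse-event documentation at the first dose of BBI608 or BBI503, whereas Section 5.4.1 and Appendix B assess events from Cycle 1, Day 1. Read literally, 8.1.1 would leave the run-in, and Arm 3 altogether, without a starting point. The passages must be reconciled.

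**What to change.** 1. Add the Study Drug Safety Population to SAP section 5 as the protocol defines it, and exempt it from the single-set rule in 7.2.4.
2. Use it as the denominator for the napabucasin- and amcasertib-related rows, each within its own arm.
3. In 7.2.4.1 add an overview and a system organ class/preferred term table for events that begin or worsen from the first napabucasin or amcasertib dose. As a descriptive reference, show Arm 3 patients still on sorafenib, counted from Day 15. Label these tables as conditional on completing the run-in.
4. Keep the any-dose and run-in tables unchanged, with the any-dose table as the comparison between arms.
5. Report by arm the number of patients who stop before the first investigational dose, or before Day 15 in Arm 3, so that the gap between the two denominators is visible.
6. Reconcile Protocol 8.1.1 with Section 5.4.1 and Appendix B on when adverse-event recording starts.

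Items 1 to 5 need SAP wording and a rerun of existing shells with one flag, with no new data beyond dates already collected. The cost is more tables, and a conditional comparison that could be over-read, hence the label. Item 6 needs a protocol clarification and a check of what sites recorded during the run-in.
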